4. OBJECTIVES AND ENDPOINTS

Table 7 Study objectives and endpoints (Amended, 23 November 2020)

Objectives	Endpoints
To evaluate VE in the prevention of HZ compared to placebo in Chinese adults ≥ 50 YOA, as measured by the reduction in HZ risk. Criterion: The objective is met if the lower limit (LL) of the 2-sided 95% confidence interval (CI) of VE is above 25%.	Confirmed HZ cases in the modified Exposed Set (mES). Refer to Section 10.2 for description of mES.
To evaluate VE in the prevention of HZ compared to placebo in subjects within each of the following age ranges: 50-69 YOA and ≥ 70 YOA, as measured by the reduction in HZ risk	Confirmed HZ cases within each of the following age ranges: 50-69 YOA and ≥ 70 YOA in the mES.
To evaluate vaccine reactogenicity and safety	
Solicited local and general adverse events (AEs) (Amended, 23 November 2020)
 
 – Occurrence, intensity and resulting in medically attended visit of each solicited local AE within 7 days (Days 1 - 7) after each vaccination – Occurrence, intensity, resulting in medically attended visit and relationship to vaccination of each solicited general AE within 7 days (Days 1 - 7) after each vaccination. 
Unsolicited AEs
 
 – Occurrence, intensity, resulting in a medically-attended visit, and relationship to vaccination of unsolicited AEs (including cellulitis) within 30 days (Days 1 - 30) post-vaccination period, according to the Medical Dictionary for Regulatory Activities (MedDRA) classification.

Objectives	Endpoints

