10.3.5. Safety analyses (Amended, 23 November 2020)

The primary analysis of safety will be performed on the Exposed Set.

All analyses will also be performed by age strata (50-69 YOA and ≥ 70 YOA).

Endpoint	Statistical Analysis Methods
Secondary	
The percentage of subjects with at least 1 local AE (solicited and unsolicited), with at least 1 general AE (solicited and unsolicited) and with any AE during the solicited follow-up period will be tabulated with exact 95% CI after each vaccine dose and overall. The percentage of doses followed by at least 1 local AE (solicited and unsolicited), by at least 1 general AE (solicited and unsolicited) and by any AE will be tabulated, with exact 95% CI. The percentage of subjects with at least 1 local AE (solicited only), with at least one general AE (solicited only) and with any AE (solicited only) during the solicited 7-day follow-up period will be tabulated with exact 95% CI after each vaccine dose and overall. The same calculations will be performed for AEs rated as grade 3.
 
The percentage of subjects reporting each individual solicited local and general AE during the solicited follow-up period will be tabulated with exact 95% CI. The percentage of doses followed by each individual solicited local and general AE will be tabulated, with exact 95% CI. Fever will be reported per 0.5°C cumulative increments and the same tabulation will be performed for fever with causal relationship to the study vaccine. For all other solicited AE, the same tabulation will be performed for grade 1, grade 2 and grade 3 AEs and for any and grade 3 general AEs with relationship to the study vaccine.
 
The proportion of solicited AEs resulting in a medically attended visit will be tabulated.
 
Duration of each individual solicited local and general AE during the solicited follow-up period will be presented. Total duration of each individual solicited local and general AE will be tabulated.

Endpoint	Statistical Analysis Methods

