5.7. Analysis of safety and reactogenicity

5.7.1. Analysis of safety and reactogenicity planned in the protocol

The primary analysis of safety will be performed on the ES. All analyses will also be performed by age strata (50-69 YOA and ≥ 70 YOA). Following analysis is planned to be performed:

The percentage of subjects with at least 1 local AE (solicited and unsolicited), with at least 1 general AE (solicited and unsolicited) and with any AE (solicited and unsolicited) during the solicited follow-up period will be tabulated with exact 95% CI after each vaccine dose and overall. The percentage of doses followed by at least 1 local AE (solicited and unsolicited), by at least 1 general AE (solicited and unsolicited) and by any AE will be tabulated, with exact 95% CI. The percentage of subjects with at least 1 local AE (solicited only), with at least one general AE (solicited only) and with any AE (solicited only) during the solicited 7-day follow-up period will be tabulated with exact 95% CI after each vaccine dose and overall.

The percentage of subjects reporting each solicited local and general AE during the solicited follow-up period will be tabulated with exact 95% CI. The percentage of doses followed by each individual solicited local and general AE will be tabulated, with exact 95% CI. Fever will be reported *with any ($>=38.0$), $>=38.0 - <=38.5$, $>38.5 - <=39.0$ and >39.0 in GSK scale. In Chinese scale, it will be reported with any ($>=37.3$), $37.3 - <38.0$, $38.0 - <38.5$, $38.5 - <39.5$ and $>=39.5$* . The same tabulation will be performed for fever with causal relationship to the study vaccine.

*In the table presented based on the GSK scale, for all other solicited AEs, the same table will have grade 1, grade 2 and *at least* grade 3 AEs and for any and *at least* grade 3 general AEs with relationship to the study vaccine. Related grade 1 and related grade 2 will also be displayed.*

In the table presented based on the Chinese scale, for all other solicited AEs, the same table will have grade 1, grade 2, grade 3 and grade 4 applicable for table with Chinese intensity scale) AEs and for any, grade 3 and grade 4 general AEs with relationship to the study vaccine. Related grade 1 and related grade 2 will also be displayed.

The proportion of solicited AEs resulting in a medically attended visit will be tabulated.

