The percentage of subjects with at least 1 report of unsolicited AE (including cellulitis) classified by MedDRA primary system organ class (SOC) and preferred terms (PT) will be reported within 30 days (Days 1-30) post each vaccination with exact 95% CI. The same tabulation will be performed for grade 3 unsolicited AEs, for unsolicited AEs with a relationship to vaccination, grade 3 unsolicited AEs with a relationship to vaccination.

Number and percentage of any, grade 3, related, grade 3 related and medically attended unsolicited AEs reported within 30 days (Days 1-30) post *any* vaccination according to MedDRA primary system organ class and preferred terms will be presented.

Number and percentage of SAEs from first vaccination up to 12 months post last vaccination will be presented with 95% CI. The same tabulation will also be done for the interval- starting from first vaccination up to 30 days post last vaccination.

Number and percentage of SAEs causally related to vaccination for the interval- starting from first vaccination up to 30 days post last vaccination and from first vaccination up to 12 months post last vaccination and from study start up to study end will be presented with 95% CI.

Number and percentage of subjects experiencing fatal SAEs, classified by MedDRA Primary System Organ Class and Preferred Term will be tabulated using date of onset of SAE for the time periods –from first vaccination up to 30 days post last vaccination and first vaccination up to 12 months post last will be presented with 95% CI.

Number and percentage of fatal SAEs causally related to vaccination for the interval- starting from first vaccination up to 30 days post last vaccination and from first vaccination up to 12 months post last vaccination and from study start up to study end will be presented with 95% CI.

Number and percentage of pIMDs from first vaccination up to 12 months post last vaccination will be presented with 95% CI. The same tabulation will also be done for the interval – starting from first vaccination up to 30 days post last vaccination.

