8. CHANGES TO THE PROTOCOL DEFINED STATISTICAL ANALYSIS

Following is the change from protocol defined statistical analysis:-

- Fatal SAEs will not be tabulated using the date of death within the same time periods.
- **CC1**
- *Grade 3 for redness/swelling will be defined as redness/swelling with diameter ≥ 100 mm in Chinese scale*
- *Preferred Terms to identify Grade 4 for swelling and redness have been added*
- *The analysis on at least 1 local AE (solicited and unsolicited; solicited only) with at least 1 general AE (solicited and unsolicited; solicited only) and with any AE (solicited and unsolicited; solicited only) during the solicited follow-up period with causal relationship with vaccine and AE rated as at least grade 3 according to GSK and Chinese scale will not be performed.*

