9.2.3. Safety

- For the analysis of HZ related complications/unsolicited AEs/SAEs/pIMDs/concomitant medication, all vaccinated subjects will be considered and subjects who did not report an event will be considered as subjects without an event.
- AEs that need to be reported as pIMDs are listed in Table 23 of the protocol. *The table presenting pIMDs, will also include the AEs considered as pIMDs as per MedDRA dictionary.*
- Assessment of intensity for solicited local and general AEs will be done separately as per GSK scale and Chinese scale. From an analysis perspective, the intensity of nausea, vomiting and diarrhoea will be presented separately as per the guidelines of Chinese authorities. In addition, as per GSK standard grading, the solicited general AEs of nausea, vomiting, diarrhoea and/or abdominal pain will be presented collectively as “gastrointestinal symptoms”.

For analysis as per GSK standard grading, the maximum intensity of any one of these solicited general AEs (i.e. nausea, vomiting and diarrhoea **and abdominal pain**) reported by a subject will be attributed as maximum intensity of “gastrointestinal symptoms” for that subject. Maximum of grade 3 and 4 will be considered as grade 3 **for all applicable solicited symptoms (not only gastrointestinal symptoms) in GSK standard grading table.**

The intensity of the following solicited AEs will be assessed as described below:

Table 3 Intensity scales for solicited symptoms in adults

Adults		
Adverse Event	Intensity grade	Parameter
Pain at injection site	0	None
	1	Mild: Do not influence or do slightly influence limb activities.
	2	Moderate Influence limb activities.
	3	Severe: Influence daily life.
	4	Lose the basic selfcare ability, or hospitalization
Redness at injection site		Record greatest surface diameter in mm
Swelling at injection site		Record greatest surface diameter in mm
Temperature*		Record temperature in °C (with 1 decimal)
Headache	0	Normal
	1	Mild: Headache that is easily tolerated
	2	Moderate: Headache that interferes with normal activity
	3	Severe: Headache that prevents normal activity
	4	Refractory; require emergency presentation or hospitalization
Fatigue	0	Normal
	1	Mild: Fatigue that is easily tolerated
	2	Moderate: Fatigue that interferes with normal activity
	3	Severe: Fatigue that prevents normal activity
	4	Emergency presentation or hospitalization
Gastrointestinal symptom (Diarrhea)	0	Normal

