10.1.2.3.2. Studies with paper diaries

For studies using paper diaries which have questions in the CRF indicating the presence or absence of solicited events, the following rules are applicable.

- *Denominators for the summary of administration site (or systemic) solicited events will be calculated using the number of participants who respond "Yes" or "No" to at least one occurrence of the specific administration site (or systemic) solicited event. If there are at least 1 non-missing value of temperature from day 1 to day 7 post vaccination, that occurrence will be counted as well in the denominator of systemic solicited events.*
- When a specific solicited event is marked as having not occurred following a specific study dose (i.e. SDTM CE.CEOCCUR=N for the specified post-dose period for the event in question), all daily measurements will be imputed as Grade 0.

- *For fever, if there are missing values and/or non-missing values of temperature from day 1 to day 7 post vaccination which are not qualifying fever definition per protocol for GSK intensity and Chinese intensity tables, then that subject would not be considered for 'Any' rows of the solicited event summary tables.*
- When a specific solicited event is marked as having occurred following a specific study dose (i.e. SDTM CE.CEOCCUR=Y for the specified post-dose period for the event in question), any missing daily recordings will be given imputed values to allow them to contribute to the 'Any' rows but not to specific grade rows of the solicited event summary tables.
- The following table shows how participants contribute to each category for a specific solicited adverse event over the Day X to Day Y post-dose period:

Solicited adverse event category	Participants included in the calculation of the numerator
Any	All participants with at least one occurrence of the adverse event at grade 1, 2, or 3 for table by GSK intensity scale and at grade 1, 2, 3 or 4 for table by Chinese intensity scale between Day X and Day Y or with the adverse event marked as present and at least one missing daily recording between Day X and Day Y
Grade 1	All participants with at least one occurrence of the adverse event at grade 1 between Day X and Day Y
Grade 2	All participants with at least one occurrence of the adverse event at grade 2 between Day X and Day Y
At least grade 3	All participants with at least grade 3 or grade 4

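### SAP section 8 drops, without a reason and in ambiguous wording, the protocol's summary of subjects and doses with at least one grade 3 AE; the tables that remain only bound it

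*SAP*

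**What the plan says.** Protocol section 10.3.5 plans a set of composite summaries over the solicited follow-up period: at least one local AE, at least one general AE, and any AE. For solicited and unsolicited events together, these are given as percentages of subjects (after each dose and overall) and of doses. For solicited events alone, they are given as percentages of subjects. All carry exact 95% CIs. The paragraph ends: "The same calculations will be performed for AEs rated as grade 3".

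SAP section 5.7.1 repeats the any-grade part and does not carry that last sentence. SAP section 8, which lists departures from the protocol analysis, has a bullet on these same composites that ends "AE rated as at least grade 3 according to GSK and Chinese scale will not be performed". Read with the words just before it, the ending is "with causal relationship with vaccine and AE rated as at least grade 3 according to GSK and Chinese scale will not be performed". It gives no reason.

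The SAP keeps four related outputs:

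- Per-symptom tables in section 5.7.1: "The percentage of subjects reporting each solicited local and general AE during the solicited follow-up period will be tabulated with exact 95% CI", broken down by grade on each scale. Section 10.1.2.3.2 defines the severe row for one specific symptom at a time: "All participants with at least grade 3 or grade 4".
- A partial composite on the GSK scale in section 9.2.3: "the solicited general AEs of nausea, vomiting, diarrhoea and/or abdominal pain will be presented collectively as" one gastrointestinal item, at the subject's maximum intensity.
- A table of unsolicited events over Days 1-30: "The same tabulation will be performed for grade 3 unsolicited AEs".
- Durations of severe solicited events, in section 5.7.2.

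**The concern.** Reactogenicity is a secondary objective, and intensity is part of its endpoints. The share of vaccinees with at least one severe reaction is a figure that readers of a reactogenicity report commonly look for, and the protocol planned to supply it with a CI for each group. The SAP keeps the any-grade composite and shows related grade 1 and related grade 2 rows per symptom, but drops the severe composite and does not say why.

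The remaining rows do not replace it. One subject with severe fatigue, headache and myalgia counts in three rows, so adding rows counts people more than once. The wording of the bullet adds a second difficulty: a programmer cannot tell with certainty which analysis has been removed.

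**Working it through.** **Step 1. What the bullet removes.** The words about causal relationship and the words about grade are joined by 'and', which allows two readings.

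- Narrow: only the version that is both related and at least grade 3 is dropped. But protocol section 10.3.5 plans no related version of these composites, so the SAP would be dropping something never planned. The protocol's grade 3 version would then be missing from SAP section 5.7.1 without being declared.
- Broad: a related version and an at-least-grade-3 version are both dropped. This fits the missing sentence in section 5.7.1.

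The broad reading is the more likely. Under either reading the text needs correcting.

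**Step 2. Can the kept tables recover the figure?** No stated figure exists to reproduce. For symptom rates p_i, the share with at least one is bounded by

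max(p_i) ≤ P(at least one) ≤ min(1, Σ p_i).

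The lower end is full overlap and the upper end is no overlap.

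Inputs: 3 solicited local symptoms (protocol Table 23), 9 solicited general symptoms (Table 24), and about 3069 subjects per group (section 7.2.2.2.1). The row rates of 1% and 2% are assumptions, because the documents give no grade 3 rates.

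| Summary | Rows | At 1% per row | At 2% per row |
|---|---|---|---|
| Any local | 3 | 1% to 3% (31 to 92 of 3069) | 2% to 6% (61 to 184) |
| Any general, separate rows | 9 | 1% to 9% (31 to 276) | 2% to 18% (61 to 552) |
| Any solicited, separate rows | 12 | 1% to 12% (31 to 368) | 2% to 24% (61 to 737) |

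**Step 3. Allow for the GSK-scale composite.** It gives the exact union for four general symptoms (nausea, vomiting, diarrhoea, abdominal pain). Call its rate c. Five rows remain: fatigue, fever, headache, myalgia and shivering.

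- At 2% per symptom, c lies between 2% and 4 × 2% = 8%. Any severe general AE lies between c and c + 5 × 2% = c + 10 points: 2% to 12% if c = 2%, and 8% to 18% if c = 8%.
- At 1% per symptom, the range is c to c + 5 points.

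The composite narrows the range from 16 points to 10 (from 8 to 5 at 1%) but does not close it.

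**Step 4. Chinese scale.** The 2% to 18% range uses the Chinese-scale rows alone and assumes that all nine symptoms have a row there. Protocol Table 24 notes that abdominal pain and shivering are not in the Chinese criteria. If those two were left out, seven rows would give 2% to 7 × 2% = 14%.

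**Step 5. Unsolicited events.** The grade 3 unsolicited table covers a different class of event over 30 days, whereas the protocol's composite is over the solicited period. It cannot be combined with the symptom rows to give the any-AE figure.

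**The case against.** The strongest reply is that nothing is lost or hidden. Several parts of it stand.

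- The removal is declared under the heading meant for such changes.
- The listed endpoints are per symptom: for local events, "Occurrence, intensity and resulting in medically attended visit of each solicited local AE within 7 days (Days 1 - 7) after each vaccination", with a parallel wording for general events. The kept rows answer them. A composite of any grade 3 event is not a listed endpoint.
- Grades are still derived per subject. Section 5.1 makes subject-level data available after the analyses are complete, and section 7.1 puts individual listings in the study report.
- The bounds rest on assumed rates, and their ends are limiting cases.
- The list of tables is a separate document (SAP section 10.2), so a surviving table there cannot be ruled out.

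A reader might therefore infer too much from the bullet: that the trial cannot report how many subjects had a severe reaction, that a secondary endpoint goes unanalysed, or that only single-symptom severity rows remain. The documents support none of these. The count is derivable, the endpoints are covered, and the SAP keeps the gastrointestinal composite and the unsolicited grade 3 table.

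What the reply does not supply is a reason for the removal, or a planned output that gives the figure. Declaring a change does not explain it.

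**Conclusion.** The point holds as a modest one. The SAP removes a severity summary that the protocol planned, without a reason, in a bullet that can be read two ways. No solicited table described in the SAP text gives the figure. At an assumed 2% per symptom, the reader would be left with a range of 16 points for any severe general AE from the nine Chinese-scale rows, or 10 points on the GSK scale with the composite; at 1%, 8 and 5 points.

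The conclusion rests on the broad reading of the bullet, which the omission in section 5.7.1 makes the more likely one, and on the SAP text alone, since the table list was not available. It concerns planned reporting only: the data are collected and the primary analysis is untouched.

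**What to change.** Reword the SAP section 8 bullet so that it clearly drops only the version restricted to events related to vaccination.

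Restore in SAP section 5.7.1 the summary of at-least-grade-3 events:

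- for local, general and any AE;
- for solicited plus unsolicited, and for solicited only;
- as percentages of subjects after each dose and overall, and as percentages of doses where protocol section 10.3.5 plans them;
- on the GSK scale and on the Chinese scale, by group, with exact 95% CIs. State which symptoms enter the Chinese-scale composite.

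Add the tables to the separate table list. If the sponsor prefers to keep the removal, section 8 should say exactly what is removed and why.

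The cost is a few extra tables from grades already derived. No new data are needed, and no other analysis changes.

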9. NON-STANDARD DATA DERIVATION RULES AND STATISTICAL METHODS

The following sections describe additional derivation rules and statistical methods which are not presented in section 10.1.

9.1. Data derivation

9.1.1. Demography

For computation of age, following rule need to be considered:

- Age will be calculated as the number of years between the date of birth and the date of first vaccination.
- To ensure that the collection of date of birth will not jeopardise the privacy of Personal Identifiable Information (PII), only a partial date of birth (YYYY) will be collected. As the date and month will be missing, the date will be replaced by the June 30th of the year.

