6. STUDY POPULATION

6.1. Inclusion criteria for enrolment

Deviations from inclusion criteria are not allowed because they can potentially jeopardize the scientific integrity, regulatory acceptability of the study or subject safety. Therefore, adherence to the criteria as specified in the protocol is essential.

All subjects must satisfy ALL the following criteria at study entry:

- Subjects who, in the opinion of the investigator, can and will comply with the requirements of the protocol (e.g. completion of the diary cards, return for follow-up visits) or/and subjects' Legally Acceptable Representative(s) [LAR(s)] who, in the opinion of the investigator, can and will comply, with the requirements of the protocol (e.g. completion of the diary cards, return for follow-up visits).
- Written or witnessed/thumb printed informed consent obtained from the subject/subject's LAR prior to performance of any study specific procedure.
- A male or female aged 50 years or older at the time of the first vaccination.
- Medically stable subjects as established by medical history and history-directed clinical examination before entering into the study.
- Female subjects of non-childbearing potential may be enrolled in the study. Non-childbearing potential is defined as current bilateral tubal ligation or occlusion, hysterectomy, bilateral ovariectomy or post-menopause. Please refer to Section [12.6.1](#) for definitions of menopause.
- Female subjects of childbearing potential may be enrolled in the study, if the subject
 - has practiced adequate contraception for 30 days prior to vaccination, and
 - has a negative pregnancy test on the day of vaccination, and
 - has agreed to continue adequate contraception during the entire treatment period and for 2 months after completion of the vaccination series.

Refer to Section [12.6.1.1](#) for definitions of woman of child bearing potential and adequate contraception.

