7.2.2.2.1. Study group and treatment number allocation

The target will be to enrol approximately 6138 eligible subjects who will be randomly assigned to 2 study groups in a (1:1) ratio (approximately 3069 subjects in each group).

The enrolment will be performed to ensure distribution of the population across the 2 age strata (50-69 YOA and ≥ 70 YOA). Approximately 75-80% and 20-25% subject should be enrolled in 50-69 YOA and ≥ 70 YOA, respectively. The expected distribution of subjects within these 2 age strata is as shown in Table 12.

To ensure that the collection of date of birth will not jeopardize the privacy of Personally Identifiable Information (PII), only year of birth (YYYY) will be collected.

Table 12 Number of subjects required for enrolment

Age Stratum	Vaccine	Targeted number (%) of subjects
50-69 YOA	RZV	4604-4910 (75-80%)
	Placebo	
≥ 70 YOA	RZV	1228-1534 (20-25%)
	Placebo	

Allocation of the subject to a study group at the investigator site will be performed using a randomization system on internet (SBIR). Within each age stratum, the randomization algorithm will use a minimization procedure accounting for center, gender, age (50-59, 60-69 for 50-69 YOA stratum, 70-79 and ≥80 YOA for ≥ 70 YOA stratum) and a combined minimization factor to reflect the presence of any of the following conditions: type 2 diabetes mellitus, asthma, chronic obstructive pulmonary disease, chronic kidney disease and depression. Minimization factors will have equal weight in the minimization algorithm.

After obtaining the signed and dated ICF from the subject/subject's LAR and having checked the eligibility of the subject, the study staff in charge of the vaccine administration will access SBIR. Upon the subject identification number, the randomization system will determine the study group and will provide the treatment number to be used for the first dose.

The number of each administered treatment must be recorded in the eCRF on the Vaccine Administration screen.

When SBIR is not available, please refer to the SBIR user guide or the Study Procedures Manual (SPM) for specific instructions.

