5.3.2. Additional considerations

Following additional tables will also be generated:

- Number of subjects by centers will be presented on ES.
- ***Deviation from protocol-defined age and visit interval on ES.***
- The following table will be generated for web disclosure:
 - Percentage of enrolled subjects by age categories (18-64, 65-84, ≥ 85) YOA will be tabulated by group.
- Summary of important protocol deviations leading to elimination from any analysis will be presented for the Enrolled Set overall and by age strata.
- The number of subjects enrolled into the study as well as the number of subjects excluded from ***mES and PPS*** analyses will be presented through 3 consort tables, overall and by age strata only for Consort table 1 and 2:
 - Consort table 1 - Showing the subjects disposition from Enrolled Set to ES
 - Consort table 2 – Showing the subjects disposition from ES to mES
 - Consort table 3 - Showing the subjects disposition from ES to PPS

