5.5.2. Additional considerations

Following descriptive table and figure will be generated by study groups on mES and ES:

- For each study group, the number of subjects at risk, person-year, number and incidence of confirmed HZ will be tabulated overall.
- Forest plot for vaccine efficacy against HZ by age strata and overall during the entire study period
- ***Cumulative incidence curve for HZ for each study group.***
- Number and percentage of episodes of all confirmed HZ episodes during the entire study period.
- Number and percentage of confirmed HZ episodes out of all the suspected cases reported.
- Number and percentage of suspected cases for which at least one PCR sample was collected on ES only.
- Distribution of suspected HZ cases using the HZ classification tools (PCR testing & HZ Ascertainment Committee (HZAC))
- The vaccine efficacy will be assessed by Poisson method for primary objective and fitted via the PROC GENMOD procedure according to the following code

```
PROC GENMOD DATA=pois_ve EXACTONLY;  
BY AGECAT;  
STRATA AGECAT;  
CLASS AGECAT/PARAM=ref;  
MODEL nb_cases = group_nb/DIST=poisson OFFSET = Log_T LINK=log;  
EXACT group_nb /ESTIMATE OUTDIST=dist ALPHA=0.05;  
ODS OUTPUT ExactParmEst=estimate ExactTests=ExactTest;  
RUN;
```

Where,

nb_case = number of cases

[figure not shown]
agecat = Age strata categories (50-69 and \geq 70 YOA)

group_nb = Group information of the subject (treatment received by subject)

Log_T = Log of the follow-up time

```
DATA VE ;  
SET ESTIMATE;  
FORMAT VE best12. ll best12. ul best12.;  
VE = ( 1 - exp (estimate)) * 100;  
ll = ( 1 - exp (UPPERCL)) * 100;  
ul = ( 1 - exp (LOWERCL)) * 100;  
RUN;
```

CCI

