10.1.3. Data derivation

10.1.3.1. Age at first dose in years

When age at first dose is to be displayed in years, it will be calculated as the number of complete calendar years between the date of birth and the date of first dose. For example:

DOB = 10SEP1983, Date of first dose = 09SEP2018 -> Age = 34 years

DOB = 10SEP1983, Date of first dose = 10SEP2018 -> Age = 35 years

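### Does imputing 30 June as the birthday put subjects in the wrong age stratum, or make eligible 50-year-olds look under age?

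*SAP*

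**What the plan says.** Protocol section 7.2.2.2.1 states that, for privacy, "only year of birth (YYYY) will be collected". SAP section 9.1.1, under the heading Demography, gives the rule for computing age: "Age will be calculated as the number of years between the date of birth and the date of first vaccination". It then deals with the missing part of the birth date: "As the date and month will be missing, the date will be replaced by the June 30th of the year". SAP section 10.1.3.1 adds that, when age is shown in years, "it will be calculated as the number of complete calendar years between the date of birth and the date of first dose". The 30 June choice matches the SAP's general rule in section 10.1.2.1 for a date with day and month missing.

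Eligibility rests on actual age: "A male or female aged 50 years or older at the time of the first vaccination" (Protocol section 6.1). The site checks eligibility first and then enters the randomisation system, which allocates within the strata 50-69 and 70 or older (Protocol section 7.2.2.2.1).

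The efficacy code in SAP section 5.5.2 uses a variable AGECAT, whose key begins "agecat = Age strata categories (50-69 and" and goes on to 70 or older. Its source is not given. SAP section 5.3.2 adds a descriptive table: "Deviation from protocol-defined age and visit interval on ES". It does not say which age that table uses.

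**The concern.** With a year-only birth date, every subject's birthday becomes 30 June. Someone born in early 1971 and vaccinated on 14 May 2021 is truly 50 and eligible, but computes as 49. That subject could appear in the age-deviation table although correctly enrolled, and has no AGECAT level, since the lowest begins at 50. At the other boundary, subjects near 70 could be moved between strata.

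AGECAT enters the primary efficacy model, defines the secondary efficacy objective by age, and splits the safety tables. If it came from derived age, analysis strata could disagree with randomisation strata, and a careless program could drop a subject with a computed age of 49.

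**Working it through.** **The plan's own figures.** Protocol Table 12 follows from 6138 planned subjects: 6138 × 0.20 = 1227.6 and 6138 × 0.25 = 1534.5 (stated 1228-1534); 6138 × 0.75 = 4603.5 and 6138 × 0.80 = 4910.4 (stated 4604-4910). They agree. The two worked ages in SAP section 10.1.3.1 (34 and 35) also reproduce.

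**Share of a boundary birth year aged wrongly.** Assume birthdays uniform over 365 days, and let d be the day of the year of vaccination. Before 30 June (day 181) the wrongly aged are those whose birthday has passed, d/365. From 30 June they are those whose birthday is still to come, (365 − d)/365. At the first-visit dates in SAP section 9.2.3:

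| First visit, 2021 | Calculation | Wrongly aged |
|---|---|---|
| 14 May | 134/365 | 36.7% |
| 6 June | 157/365 | 43.0% |
| 15 July | 169/365 | 46.3% |
| 21 July | 163/365 | 44.7% |
| 11 September | 111/365 | 30.4% |
| 15 September | 107/365 | 29.3% |

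These are opening days, not averages over enrolment. The share falls to about 17% by 31 October and to zero by 31 December.

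**At age 50.** Only subjects whose birthday has passed and who are vaccinated before 30 June compute as 49. They are 36.7% of true 50-year-olds on 14 May and 49.3% on 29 June (180/365); the others compute correctly as 50. From 30 June to the end of 2021 nobody truly 50 computes as 49. Four of the six listed centres opened after 30 June 2021. The documents do not give the end of enrolment, so assume 5% to 33% of subjects were vaccinated before a 30 June, and 3.75% to 4% of subjects per single year of age:
- low: 6138 × 0.05 × 0.0375 × 0.367 = 4.2
- high: 6138 × 0.33 × 0.04 × 0.493 = 39.9

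**At age 70.** Before 30 June some true 70-year-olds compute as 69; afterwards some true 69-year-olds compute as 70. Assume 1% to 4% of subjects per single year of age near 70 and 15% to 50% of them misaged:
- low: 6138 × 0.01 × 0.15 = 9.2 (0.15% of the trial)
- high: 6138 × 0.04 × 0.50 = 122.8 (2.0%)

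**Cases moved.** Protocol section 10.1.2 assumes a placebo attack rate of 0.85% per year and 85% efficacy. With half of the moved subjects in each group, the upper end gives 61.4 × 0.0085 × (1 + 0.15) = 0.60 cases per year of follow-up; the lower end gives 4.6 × 0.0085 × 1.15 = 0.04.

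**Effect on efficacy at 70 or older.** With equal efficacy in both strata, moving subjects leaves the expected stratum estimate unchanged. As a harsher illustration, take 97.2% for the younger stratum and 89.8% for the older (the figures in Protocol section 3.1, although the first refers to everyone 50 or older). Put 22.5% of subjects in the older stratum, 0.225 × 6138/2 = 690.5 per group, and move 60 younger subjects per group into it. At a common placebo rate, efficacy becomes 1 − (690.5 × 0.102 + 60 × 0.028)/(690.5 + 60) = 90.4%. Moving 30 per group gives 90.1%. With assumed placebo rates of 0.75% and 1.15% per year, the results are 90.2% and 90.0%.

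**Who could be dropped.** SAP section 5.5.1.1 says that every subject in the modified Exposed Set contributes to the primary comparison. The elimination codes for that set (SAP section 4.2.3.1) include none for age or eligibility. Code 2010, for eligibility violations, is listed only for the Per Protocol Set (section 4.2.4.1).

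**The case for a change.** The strongest case for a change is that a stratification variable in a confirmatory analysis should have one stated source. Two programmers could build AGECAT differently from this text. The randomised stratum exists for every subject, agrees with the allocation by construction, and would take one sentence to name. A correctly enrolled subject shown as an age deviation is a false statement in a report. If code 2010 were driven by derived age, that subject would also leave the Per Protocol Set.

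Some of this stands: the source of AGECAT and of the age-deviation table is unstated, and naming it would do no harm. The rest is inference. Section 9.1.1 never mentions strata, and AGECAT has the same cut-points as the randomisation strata, so reading it as the randomised stratum is at least as natural. Nor is that stratum known to be more accurate. The documents do not say what age information the randomisation system uses, and year-only collection is stated in the same protocol section as the allocation. The claim that a subject would be lost assumes a program that contradicts SAP section 5.5.1.1. For the deviation table, flagging only those who could not be 50 on any birthday in their birth year would miss some who truly were 49. With a year-only date, each rule misses or over-reports someone.

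**Conclusion.** The mechanism is real: the 30 June rule can turn an eligible 50-year-old into a computed 49 and can move subjects across 70. It does not follow that the plan misplaces or loses anyone. What remains is a missing detail that an analyst would fill sensibly, by using the randomised stratum or by assigning a confirmed-eligible subject with a computed age of 49 to the younger stratum.

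The worst plausible size is small: about 4 to 40 subjects computed as 49, and about 9 to 123 crossing 70, at most 2.0% of 6138. Fewer than one zoster case per year of follow-up is expected to move. The shift is unrelated to treatment, so overall efficacy is essentially untouched, and in the harsher illustration efficacy at 70 or older moves from 89.8% to between 90.0% and 90.4%. The by-age efficacy results are descriptive (Protocol section 10.1.1, SAP section 6), and the age-deviation table carries no exclusion from the Exposed Set or the modified Exposed Set. Year-only birth data is a deliberate privacy choice, and the imputation follows the SAP's general date rule.

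These sizes rest on uniform birthdays and on assumed shares of subjects per year of age and vaccinated before 30 June, none of which the documents give. No change to the plan is needed.
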